## 2.2 TRIAL OBJECTIVES

The overall objective of this trial is to evaluate the safety and anti-tumour activity of Xentuzumab (BI 836845) combined with afatinib in patients with EGFR mutant lung cancer.

### 2.2.1 Primary objectives

#### Part A – Dose confirmation:

- To determine the Maximum Tolerated Dose (MTD) and/or Recommended Phase II Dose (RP2D) of Xentuzumab (BI 836845) in combination with afatinib in patients with non-small cell lung cancer with progression following prior treatment (EGFR TKIs or platinum-based chemotherapy)

#### Part B – Expansion cohorts:

- To evaluate the early anti-tumour activity of Xentuzumab (BI 836845) in combination with afatinib in patients with EGFR mutant non-small cell lung cancer with progression following prior irreversible EGFR TKIs

### 2.2.2 Secondary objectives

#### Part A and Part B:

- To evaluate the safety of Xentuzumab (BI 836845) in combination with afatinib in patients with non-small cell lung cancer

For details on endpoints and their assessments, see [Section 5](#).

## 2.3 BENEFIT - RISK ASSESSMENT

Most patients with EGFR mutant NSCLC will develop acquired resistance to EGFR TKI despite initial benefit. Consequently, most patients with locally advanced or metastatic tumours will succumb to their disease. Thus, there is a substantial need for novel therapeutic strategies to improve the outcome for patients with advanced or metastatic EGFR mutant NSCLC.

Aberrant ErbB (HER) family expression and signalling contribute to the malignant phenotype in many tumour types including squamous cell carcinoma of lung. It is therefore expected that treatment with an ErbB family blocker may result in tumour control. Afatinib is a potent, irreversible, orally available ErbB family blocker studied in more than 3000 patients to date. The combination of afatinib with Xentuzumab (BI 836845) may further improve EGFR/ErbB1 target inhibition and overcome acquired resistance to EGFR TKIs.

Proprietary confidential information.

© 2016 Boehringer Ingelheim International GmbH or one or more of its affiliated companies. All rights reserved.

This document may not - in full or in part - be passed on, reproduced, published or otherwise used without prior written permission.

Based on toxicological findings and the experience with other EGFR (ErbB1) and HER2 (ErbB2) inhibitors, as well as results from Phase I studies, the risks of anti-EGFR/HER2 therapy with afatinib primarily consist of gastrointestinal (GI) AEs (including diarrhoea, nausea, and vomiting), and skin AEs. Skin and subcutaneous tissue disorders primarily consist of erythematous, maculo-papular and papular skin rashes, pruritus, acne, eczema, folliculitis, and pustular rash.

Xentuzumab (BI 836845) has been tested in two separate Phase I clinical trials. As of the database cut-off date of July 10, 2013, 81 patients received Xentuzumab (BI 836845) monotherapy. The AE profile observed has generally been consistent with the underlying neoplastic conditions with most AEs being CTCAE grade 1 or 2. As the clinical experience with Xentuzumab (BI 836845) is limited, safety will be carefully monitored throughout the duration of treatment with Xentuzumab (BI 836845); supportive treatments, and/or dose modification/discontinuation of Xentuzumab (BI 836845) will be mandated as necessary.

Although Xentuzumab (BI 836845) is a fully humanised antibody given intravenously, there may be a potential for infusion-related reactions and immune responses to occur. Such infusion reactions will be graded and treated following standard of care or local guidance. Out of 81 patients who received Xentuzumab (BI 836845), no infusion reaction has been observed ([U10-2830](#)). The immune responses to Xentuzumab (BI 836845) mAb will be assessed through measurement of anti-drug antibodies in the study.

Because IGF-1R signalling could be a compensatory pathway to EGFR inhibition, and IGF-1R shares a similar downstream effector pathway, AEs, e.g. cutaneous side effects and diarrhoea due to afatinib might be augmented by combining afatinib and Xentuzumab (BI 836845). Nevertheless, these side effects are not expected to become life-threatening as they can be identified early and treated appropriately with comprehensive supportive treatment and/or interruption or dose adaptation of the study treatment. In this study, detailed recommendations on management of expected side effects of afatinib will be provided to minimize the intensity and duration of side effects.

Weight loss should be monitored closely. Nutritional consultation may be recommended early and nutrition support including tube feeding or total parenteral nutrition should be provided if indicated.

Although rare, a potential for drug-induced liver injury (DILI) is under constant surveillance by sponsors and regulators. Therefore, this study requires timely detection, evaluation, and follow-up of laboratory alterations of selected liver laboratory parameters to ensure patients safety.

Given the high unmet medical need in NSCLC, the potential benefits to be expected from afatinib in combination with Xentuzumab (BI 836845) are likely to outweigh its risks in this study population.

### 3. DESCRIPTION OF DESIGN AND TRIAL POPULATION

#### 3.1 OVERALL TRIAL DESIGN AND PLAN

This is a multi-centre, open-label, phase Ib clinical trial to evaluate the safety, tolerability and anti-tumour activity of the combination of Xentuzumab (BI 836845) and afatinib. This trial will consist of a dose confirmation part (Part A) and an expansion part (Part B). Part A and Part B will be conducted sequentially.

Initially, recruitment in Part A will follow an escalation/de-escalation “3+3” design ([R07-0220](#)) to determine the Maximum Tolerated Dose (MTD) and/or recommended dose for Part B of Xentuzumab (BI 836845) in combination with afatinib in patients with NSCLC who have had progression following prior treatment (EGFR TKIs or platinum-based chemotherapy). The starting dose of afatinib will be one level below the registered dose and for Xentuzumab (BI 836845) the current monotherapy RP2D will be used. The safety of the RP2D of Xentuzumab (BI 836845) in combination with afatinib will be confirmed in a total of 12 patients across. Thus, 6 additional patients will be treated at the MTD/RP2D dose level.

After conclusion of Part A (determination of RP2D), Part B of the trial will commence in one expansion cohort to evaluate the safety, tolerability and preliminary anti-tumour activity in patients with EGFR mutant non-small cell lung cancer who have progressed on irreversible EGFR TKIs (e.g. afatinib, dacomitinib). In the expansion cohort, 18 additional patients will be treated.

Patients are enrolled in the study once the informed consent form is signed. The screening period will be up to 6 weeks (42 days) during which time the eligibility will be confirmed. In order to meet the eligibility criteria regarding EGFR genotypes and/or to characterize resistance mechanisms, all patients need to provide archived tumour sample which is associated with EGFR TKI (or other treatment in EGFR wild type) resistance or undergo a fresh tumour biopsy. In the Part B, the EGFR genotypes must be confirmed by the authorized central laboratory. The eligibility criteria will be reconfirmed prior to the first administration of study medications. Eligible patients will be treated continuously with the study regimen in the absence of disease progression, intolerable adverse events, or other reason necessitating withdrawal (refer to [Section 3.3.4](#)). The treatment will be administered as courses of 28 days. Continued treatment beyond disease progression will not be allowed in the study.

All patients will have regular assessment of safety parameters as detailed in the [Flow Chart](#).

Tumour assessment by imaging according to [RECIST version 1.1](#) will be conducted at baseline and at fixed time points as specified in the Flow Chart.

An End of Treatment (EOT) visit is to be completed when a patient permanently discontinues both study drugs, for any reason listed in Section 3.3.4.

[figure not shown]
Proprietary confidential information.

© 2016 Boehringer Ingelheim International GmbH or one or more of its affiliated companies. All rights reserved.

This document may not - in full or in part - be passed on, reproduced, published or otherwise used without prior written permission.

The assessments required are listed in the [Flow Chart](#). Patients who permanently discontinue both study drugs due to other reason than progressive disease will continue to have tumour assessments according to the Flow Chart until disease progression, lost to follow-up or initiation of other anti-tumour therapy, whichever occurs first.

A Follow-up visit (FU1) will be completed 42 (+ 7) days after the last administration of study drug. Refer to the Flow Chart and Figure 3.1: 1 below for details. FU1 will be defined as the end of on-treatment period for this trial. After disease progression, patients will be monitored for vital status in the observation period (**for Part B only**).

\* Part B only: For patients who had disease progression while on afatinib less than 40 mg/day, the starting dose is the last dose of afatinib. Alternative starting dose of afatinib must be discussed and agreed by Sponsor.

Figure 3.1: 1

Study design

### 3.1.1 Administrative structure of the trial

The trial is sponsored by Boehringer Ingelheim.

Proprietary confidential information.

© 2016 Boehringer Ingelheim International GmbH or one or more of its affiliated companies. All rights reserved.

This document may not - in full or in part - be passed on, reproduced, published or otherwise used without prior written permission.

The coordinating investigator is an oncologist with experience in this type of trial and investigations. The coordinating investigator has been designated by Boehringer Ingelheim and will sign the clinical trial report. The investigators participating in the trial must have experience in diagnosing and treating patients with locally advanced or metastatic non-small cell lung cancer. Each decision on dose escalation or de-escalation steps will be taken in agreement between the Sponsor and the principal investigators at each site and safety will be closely monitored by a BI monitor or a Contract Research Organisation (CRO) appointed by BI. There will be no steering committee or data monitoring committee for this trial.

Regular teleconferences (or online meeting) will be held for decision of dose escalation, discussion of ongoing patients, discussion and determination of MTD/RP2D, and discussion of operational aspects. The participants are the investigators and BI study team. Relevant safety, laboratory, and efficacy data should be checked by on-site monitoring or review of eCRF before the teleconference. During the regular teleconferences with the investigators and study team, the next higher dose level will be determined from the progress of existing patients at the current dose level and in consideration of available AE and PK-PD data. Any potential patients for the trial will also be discussed. Conclusion of dose escalation decision should be agreed by the investigators and BI study team. All teleconference details will be documented accordingly.

BI will appoint CROs and independent service providers for special services such as central laboratory services for biomarker testing and part of bioanalytical testing, biosample collection and logistics, and Interactive Response Technologies (IRT) for trial medication assignment/logistics. The analysis of biomarker and PK will be performed by BI or a CRO appointed by BI.

On-site monitoring will be performed by BI or a Contract Research Organisation (CRO) appointed by BI.

All trial relevant documentation will be stored in the Trial master file (TMF) at BI. In addition each site will have an Investigator Site File (ISF) containing all trial documents relevant for the site.

### **3.2 DISCUSSION OF TRIAL DESIGN, INCLUDING THE CHOICE OF CONTROL GROUP**

The '3+3' dose finding design ([R07-0220](#)) for phase I clinical studies in oncology with escalating/de-escalating steps will be used to determine the MTD of Xentuzumab (BI 836845) combined with daily dosing of afatinib. No control group is needed.

As no data regarding the optimal dose for Xentuzumab (BI 836845) combined with a daily dose of afatinib exist so far, the assessment of MTD will be performed in part A prior to further exploring the anti-tumour activity of the combination regimen in Part B. In part B, for patients who had disease progression while on afatinib less than 40 mg/day, the starting dose is the last dose of afatinib. Alternative starting dose of afatinib must be discussed and agreed by Sponsor. ([P16-10813](#)).

Patients will continue trial treatment until any reason listed in [Section 3.3.4](#) is met.

### 3.3 SELECTION OF TRIAL POPULATION

Since the objective is to evaluate the tolerability of Xentuzumab (BI 836845) plus afatinib for patients with NSCLC who have failed previous treatment (EGFR TKI or platinum based chemotherapy), it is important to conduct the dose confirmation part (Part A) in a closely related patient population and to conduct the expansion part (Part B) for the exploration of a preliminary efficacy signal in a well-defined group of patients with resistance to EGFR TKIs. Squamous cell carcinoma, a subtype of NSCLC, will be also eligible in Part A because emerging data shows that afatinib provides clinical benefit in this patient group ([P15-06906](#)). Both EGFR mutant NSCLC and SCC of lung are more likely expected to obtain benefit from afatinib-based therapy. The safety and tolerability profiles of afatinib between EGFR mutant NSCLC and SCC are similar. Ideally, a clear signal whether the experimental treatment can work in truly resistant disease will be obtained; a false positive signal has a very low likelihood as no response is to be expected from resistant clones.

#### Part A

An estimated total of about 9 to 18 patients will be necessary to establish the MTD for the combination of Xentuzumab (BI 836845) plus afatinib. If 6 evaluable patients have been treated at the MTD dose level, an additional 6 patients will be recruited to determine the RP2D, i.e., a total of 12 patients with resistance to EGFR TKIs will be treated at the MTD level. If the RP2D is different from the MTD dose, a total of 12 patients should be treated at the RP2D dose prior to commencing the Part B of the study.

#### Part B

Once the RP2D has been determined, 18 additional patients will be treated in the expansion cohort of Part B. In part B, for patients who had disease progression while on afatinib less than 40 mg/day, the starting dose is the last dose of afatinib. Alternative starting dose of afatinib must be discussed and agreed by Sponsor([P16-10813](#)).

A log of all patients included into the study (i.e. having given informed consent) will be maintained in the ISF at the investigational site irrespective of whether they have been treated with investigational drug or not.

##### 3.3.1 Main diagnosis for study entry

##### 3.3.2 Inclusion criteria

1. Male or female patients aged 18 years or older
2. Patients with pathologic confirmation of advanced and/or metastatic stage IIIb/IV non-small cell carcinoma of lung

Note: In Part A and B, diagnosis is not necessarily based on the latest tumour sample. Small cell lung cancer transformation must be excluded.

Proprietary confidential information.

© 2016 Boehringer Ingelheim International GmbH or one or more of its affiliated companies. All rights reserved.

This document may not - in full or in part - be passed on, reproduced, published or otherwise used without prior written permission.

3. Documented activating EGFR mutation (exon 19 deletion, L858R, G719X, L861X). Exception: patient with squamous cell predominant histology in Part A
4. Presence of EGFR activating mutation and absence of EGFR T790M mutation in the tumour associated with the latest disease progression. Only applicable in Part B
5. Adequate fresh or archival tumour tissue at the latest disease progression immediately prior to the study entry must be made available for central EGFR mutation test and/or resistance analysis
6. Part A: Progression of disease ([RECIST v1.1](#)) while on continuous treatment with single agent EGFR TKI (e.g. erlotinib or gefitinib or afatinib) or for histology other than adenocarcinoma and without prior EGFR TKI treatment: progression of disease (RECIST v1.1) on platinum-based chemotherapy.  
Part B: Progression of disease (RECIST v1.1) while on continuous treatment with single agent of the second generation irreversible EGFR TKI (e.g. afatinib or dacomitinib).  
**Note:** In both parts, patients whose disease progresses only in the central nervous system (CNS) are not eligible
7. No intervening systemic therapy between cessation of EGFR TKI and initiation of the treatment in the study. Exception: patient with squamous cell predominant histology in Part A
8. Patients must have measurable disease per [RECIST v1.1 \(R09-0262 - Appendix 10.5\)](#) presented after tumour biopsy for the latest disease progression
9. Eastern Cooperative Oncology Group (ECOG) performance score 0 or 1 (Refer to [Appendix 10.4](#))
10. Life expectancy of  $\geq 3$  months in the opinion of the investigator
11. Fasting plasma glucose  $< 8.9$  mmol/L ( $< 160$ mg/dL) and HbA1C  $< 8\%$
12. Adequate organ function as defined by the following criteria:
  - LVEF  $>50\%$  or within institutional values
  - Absolute neutrophil count (ANC)  $\geq 1,500/\text{mm}^3$
  - Platelet count  $\geq 100,000/\text{mm}^3$
  - Estimated creatinine clearance  $> 45\text{ml/ min}$  [Appendix 10.2](#).
  - Total bilirubin  $\leq 1.5$  times upper limit of institutional normal.
  - Aspartate amino transferase (AST) and alanine amino transferase (ALT)  $\leq 3 \times$  upper limit of institutional normal (ULN) (if related to liver metastases  $\leq 5\times$ ULN)
13. Recovered from any previous therapy related toxicity to  $\leq$  Grade 1 at study entry (except for stable sensory neuropathy  $\leq$  Grade 2 and alopecia)
14. Written informed consent that is consistent with ICH-GCP guidelines and local regulation.

Proprietary confidential information.

© 2016 Boehringer Ingelheim International GmbH or one or more of its affiliated companies. All rights reserved.  
This document may not - in full or in part - be passed on, reproduced, published or otherwise used without prior written permission.

15. No known potentially targetable mutation other than IGF signalling pathway or EGFR or no available treatment for potentially targetable mutation

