#### Protocol-specified Adverse Events of Special Interest (AESI)

The following are considered as Protocol-specified Adverse Events of Special Interest:

- Hepatic injury defined by the following alterations of liver parameters:
  - For patients with normal liver function at baseline (ALT, AST, and bilirubin within normal limits) at baseline:  
an elevation of AST and/or ALT  $\geq 3$  fold ULN combined with an elevation of total bilirubin  $\geq 2$  fold ULN measured in the same blood draw sample. Patients showing these lab abnormalities need to be followed up according to [Appendices 10.6](#) this clinical trial protocol and the “DILI checklist” provided in *ISF*.
  - For patients with abnormal liver function tests at baseline (AST and/or ALT>ULN):  
an elevation of transaminase  $\geq$  (baseline + 4 fold ULN) combined with an elevation of total bilirubin  $\geq 2$  fold ULN measured in the same blood draw sample, with the exclusion of the causes due to underlying diseases. Patients with abnormal liver function tests must have their abnormalities and the etiology documented in detail as baseline conditions. Every effort should be made to exclude the worsening of liver function due to underlying diseases.

Although rare, drug-induces liver injury is under constant surveillance by sponsors and regulators and is considered a protocol-specified significant adverse event. Timely detection, evaluation, and follow-up of laboratory alterations of selected liver laboratory parameters to distinguish an effect of the underlying malignancy on liver function from other causes are important for patient safety

- DLT occurs in the Part A. Please refer to [Section 5.2.6](#) for definition of DLTs.

Protocol-specified AESI are to be reported in an expedited manner similar to Serious Adverse Events, even if they do not meet any of the seriousness criteria – for details please see section 5.2.2.2.

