7.8.2 Laboratory data

7.8.2.1 Laboratory data

The analyses of laboratory data will be descriptive in nature and will be based on BI standards (5). The same on-treatment periods as considered for the analysis of adverse events will be applied for laboratory values except for that the baseline laboratory value will be included in the 'on-treatment' period. Patients having at least one post-baseline laboratory value will be displayed in the descriptive analyses.

Descriptive statistics, including change from baseline and frequency of patients with transitions relative to the reference range, will be provided. CTCAE grades for applicable laboratory parameters will be calculated according to CTCAE version 4.03 (10). The following outputs will be presented:

- Worst CTCAE grade experienced during the on-treatment phase.
- Transitions of CTCAE grade from baseline to worst laboratory value, from worst to last laboratory value during the on-treatment phase, and from baseline to last laboratory value.

Patients with missing CTCAE grade at baseline or no baseline value but post baseline values will be displayed in the category "Missing CTCAE grade at baseline". Laboratory values without CTCAE grading will be compared to their reference ranges and frequency tables will be provided for the number of patients within and outside the reference range at baseline and the last measurement on treatment.

Analysis of potentially clinically significant abnormal laboratory values, and handling of CTCAE grade -1 and -9 laboratory parameters, are described in the SOP for "Display and analysis of laboratory data" (5), Reference Document 9.

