7.8.2.2 Laboratory values of special interest

Hepatic enzyme elevations (potential Hy's law cases):

These are defined as those cases where a combination of all of the following events occurred: any on-treatment value of ALT and/or AST $> 3\text{ULN}$ with total bilirubin $\geq 2\text{ULN}$ and ALKP $< 2\text{ULN}$. The events can occur in any order, but must occur within 14 days of the previous event, i.e. the second event must occur within 14 days of the first event, and the third event must occur within 14 days of the second event, etc.

Patients with missing laboratory values for liver enzymes will be excluded from these analyses but will be presented separately in a listing. Tabulations of hepatic enzyme elevations and liver laboratory values (see Section 5.2.2.1 of the CTP), including flags of true DILI cases, are created in accordance with the Food and Drug Administration (FDA) DILI guidance (8).

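### The SAP's potential Hy's law count has no baseline term, so a patient with liver metastases who enters with ALT or AST above 3 and up to 5 times ULN can be counted without any transaminase rise

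*Protocol*

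**What the plan says.** **Eligibility.** Protocol 3.3.2, criterion 12, limits AST and ALT to 3 times the "upper limit of institutional normal (ULN) (if related to liver metastases", where the limit becomes 5 times ULN). Total bilirubin may be at most 1.5 "times upper limit of institutional normal".

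**Protocol hepatic-injury rule.** Protocol 5.2.2.1 (AESI) has two branches. With normal AST, ALT and bilirubin at baseline, the trigger is AST and/or ALT at least 3 ULN together with bilirubin at least 2 ULN. A second branch applies "For patients with abnormal liver function tests at baseline (AST and/or ALT>ULN"). There the transaminase must reach at least ("baseline + 4 fold ULN) combined with an elevation of total bilirubin" of at least 2 ULN. Both branches need the values in the same blood draw, and the second also excludes causes due to underlying disease. The transaminase DLT criterion in Protocol 5.2.6 adds 4 ULN to a raised baseline in the same way.

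**SAP screen.** SAP 7.8.2.2 starts from "any on-treatment value of ALT and/or AST" above 3 ULN, combined with total bilirubin at least 2 ULN and ALKP below 2 ULN. The components may come in any order, but each "must occur within 14 days of the previous event". No baseline value enters the definition.

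**On-treatment period for laboratory data.** SAP 7.8.2.1 uses the adverse-event periods, "except for that the baseline laboratory value will be included in the 'on-treatment' period".

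**Other liver outputs.** SAP 7.8.1 reports the incidence of the protocol-specified AESIs. SAP 7.8.2.2 cites Protocol 5.2.2.1 for its liver tabulations and plans flags for true DILI cases.

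**The concern.** The protocol allows raised transaminases at entry when liver metastases explain them, and its hepatic-injury and DLT rules adjust for that. The SAP's potential Hy's law definition does not. For a patient who starts above the cut-off, the transaminase component is met before the first dose, and the classification then depends only on bilirubin and ALKP.

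Because the baseline value counts as on-treatment, the pre-dose ALT or AST can itself be the qualifying value, even if the transaminase then falls below 3 ULN.

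At stake is how a safety count is read. Protocol 5.2.2.1 stresses separating effects of the malignancy on the liver from other causes. In a small trial with no control arm, one reported potential Hy's law case draws attention, and as planned the count would not show whether its transaminase component arose on treatment or was present at entry.

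**Working it through.** The plan states no figure for this point, so there is nothing to reproduce. The check applies the two rules to the same patients, in multiples of ULN.

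**Inputs**
- Entry limits (Protocol 3.3.2): transaminase ≤3, or ≤5 if related to liver metastases; bilirubin ≤1.5.
- SAP rule (SAP 7.8.2.2): transaminase >3, bilirubin ≥2 and ALKP <2, each within 14 days of the previous event.
- Protocol rule for raised baseline (Protocol 5.2.2.1): transaminase ≥ baseline + 4 and bilirubin ≥2, same draw.
- Assumption: the entry limits hold for the value taken as baseline. Protocol 3.1 has eligibility reconfirmed before the first dose.

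**Step 1: transaminase rise each rule requires**

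SAP rise = 3 − baseline, to be exceeded (none if baseline is already above 3). Protocol threshold = baseline + 4.

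| Baseline | Admissible | SAP: rise needed | Protocol: threshold | Protocol: rise needed |
|---|---|---|---|---|
| 1.5 | all | >1.5 | 5.5 | 4 |
| 2 | all | >1 | 6 | 4 |
| 3 | all | >0 | 7 | 4 |
| 3.01 | liver metastases only | none | 7.01 | 4 |
| 4 | liver metastases only | none | 8 | 4 |
| 5 | liver metastases only | none | 9 | 4 |

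The SAP needs no rise only in the last three rows. At exactly 3.0 an unchanged value fails, because 3.0 is not above 3. At 2.9 a rise of just over 0.1 is needed (0.1/2.9 = 3.4%): small, but a rise.

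**Step 2: the other components, with transaminase unchanged at 4**
- Bilirubin 1.5 (the entry limit), ALKP 1.5: not counted.
- Bilirubin 2.0, ALKP 2.5: not counted.
- Bilirubin 2.0, ALKP 1.5: counted by the SAP; not met under the protocol, which needs 8.

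Bilirubin must therefore rise from at most 1.5 to at least 2 ULN with ALKP below 2 ULN.

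**Step 3: effect of counting the baseline value**

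The Flow Chart schedules safety laboratory tests on Days 1 and 8 of Course 1. Take pre-dose ALT 4 on Day 1, then ALT 2.5, bilirubin 2.0 and ALKP 1.5 on Day 8. The pre-dose ALT exceeds 3 and counts as on-treatment, and the other components follow within 7 days. The patient is counted although ALT fell by 1.5 ULN. This example depends on carrying the 7.8.2.1 convention into 7.8.2.2, which states no other. The unchanged-value case in Step 2 does not depend on it.

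**Step 4: how many patients**

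The documents do not give the share entering above 3 ULN. Assumed shares of 1%, 2%, 5% and 10% of 42 give 0.4, 0.8, 2.1 and 4.2 patients starting above the cut-off. Each would still need the bilirubin and ALKP conditions. One counted case is 1/18 = 5.6% of Part B or 1/42 = 2.4% of the trial; these percentages scale one case and do not estimate frequency.

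**The case against.** The best defence is that the SAP count is a deliberately sensitive screen for potential cases, while the AESI rule serves expedited reporting. The two already differ on >3 versus ≥3 ULN, on 14-day windows versus the same draw, and on the ALKP condition, so a difference between them is not in itself an error. The SAP says its tabulations follow the DILI guidance it cites. That guidance is not available here, and nothing in the documents shows that a flat cut-off departs from it. This part stands: the 3 ULN cut-off need not be abandoned.

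A reader might infer that the SAP ignores the protocol's rule. It does not. SAP 7.8.1 reports the AESIs defined in Protocol 5.2.2.1, SAP 7.8.2.2 cites that section, and SAP 7.8.2.1 tabulates CTCAE transitions from baseline. But none of these changes the Hy's law definition or links its count to a patient's baseline, so the point survives.

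It is also tempting to replace the cut-off with baseline + 4 ULN for everyone above ULN. That would remove real rises from the main table. A patient going from 1.1 to 5.0 ULN, more than a fourfold increase, would miss the threshold of 1.1 + 4 = 5.1. The objection to that remedy is sound.

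Finally, the analyses are descriptive (Protocol 7.2), and the documents do not make any primary endpoint or DLT decision depend on this count. That limits the consequence but does not justify counting a pre-dose elevation as an on-treatment one.

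**Conclusion.** The point holds, within narrow limits. A patient with liver metastases who enters above 3 and up to 5 ULN can be counted as a potential Hy's law case with an unchanged or falling transaminase, where the protocol's rule would need above 7 and up to 9 ULN.

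Two wider readings are not supported. Patients admitted under the 3 ULN limit cannot be counted without a rise. Nor are those counted free of liver change, since bilirubin must have risen to at least 2 ULN.

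The number affected is unknown and may be zero. The conclusion rests on the entry limits being respected at baseline and, for the case where the transaminase falls to 3 ULN or below, on the on-treatment convention of SAP 7.8.2.1 applying in 7.8.2.2. The change belongs in SAP 7.8.2.2; inclusion criterion 12 needs none. It is worth making because it is cheap and affects how a visible safety count is read.

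**What to change.** In SAP 7.8.2.2:

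1. Keep ALT and/or AST above 3 ULN, with the existing bilirubin and ALKP conditions, as the main table.
2. Require the qualifying ALT or AST value to be post-baseline, notwithstanding the convention in SAP 7.8.2.1. The Step 3 patient then drops out. No patient with a qualifying post-baseline transaminase is lost.
3. Present the counts by baseline AST/ALT: ≤ULN, >ULN to 3 ULN, and >3 ULN. The patient unchanged at 4 ULN stays in the table, but visibly in the top stratum.
4. For each case with raised baseline, list the baseline value and whether the baseline-adjusted rule of Protocol 5.2.2.1 is also met. This reconciles the count with the AESI output patient by patient.

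The cost is a few sentences, a small programming change, and a slightly longer table and listing with very small strata. Data collection and patient management are unaffected.
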